8. DATA ANALYSIS AND STATISTICAL CONSIDERATION

8.1. Sample Size Determination

The sample size of up to 200 subjects was selected based on a goal for the registry to be able to obtain performance and safety associated with use of the VeriSight catheter. This study is observational. Outcomes remain in the exploratory phase, and therefore hypotheses will not be created. Instead, the study will serve to monitor, measure, and evaluate outcomes as a basis for future research. This sample size will provide the opportunity to make proper statistical inference for hypothesis generation. Due to the various procedure types available for use with VeriSight, up to 200 subjects could be enrolled in order to analyze the secondary endpoints by case type.

8.2. Populations for Analyses

All subjects age 18 and older that are scheduled for and will undergo a planned cardiac interventional percutaneous procedure in which the guidance of ICE is indicated, eligible and willing to sign an informed consent without meeting any of the exclusion criteria set and meeting all the inclusion criteria set forth in the protocol will be included in the population for analyses. Those who sign consent but do not undergo a cardiac procedure utilizing the Philips ICE catheter will be excluded from the analyses (screen failures).

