4.2. Exclusion Criteria

Patients who have ANY of the following exclusion criteria are NOT eligible for participation on the registry.

1. Contraindicated for ICE catheter placement or patient considerations that make placement of VeriSight not technically feasible
2. If alternate access (as needed instead of femoral) is not viable
3. Known contraindicated conditions include sepsis, major coagulation abnormalities, presence of any intracardiac thrombus, presence of class IV angina or heart failure, deep vein thrombosis, or significant peripheral vascular disease.

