4.5. Screen Failures

Only consented subjects who are considered enrolled in the registry will be followed. Those who provide consent, but then are determined to be ineligible at the time of enrollment will be considered screen failures.

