6.2. Schedule of Activities (SOA)

Table 1 provides an overview of registry procedures per visit.

Document ID:	IGT_IGD_ICE Registry Study_2019_10745	Document title:		Classification:	Confidential
Modified:	24 APR 2021	Philips ICE Registry			
Version:	2.0	User Tool ID:	16.2.6UserTool0004	Page:	19
Status:	Final	User Tool Version Date	30May2019		

Clinical Registry Protocol
IGT_IGD_ICE Registry Study_2019_10745

Table 1. Overview of registry procedure			
Procedures	Screening*	Index procedure	Post-Procedure (at discharge or 48hrs)
Assessment of eligibility	X		
Informed consent	X		
Record demographics	X		
Medical History and Physical (H&P)	X		
Record any baseline diagnostic imaging		X	
ICE imaging with VeriSight		X	
Image grading		X	
Procedural workflow and details		X	
Adverse device effects related to VeriSight		X	X
Registry exit			X
Usability assessment	Aggregate input		
Physical attributes of catheter	After 1 st patient enrolled	After 10 th patient enrolled	After last patient enrolled
Physician and staff survey	After 1 st patient enrolled	After 10 th patient enrolled	After last patient enrolled

*up to 30 days prior to index

Below are the brief study procedure steps.

- Subjects are evaluated for eligibility based on the inclusion and exclusion criteria
- Record demographics of subjects: age, gender, height, weight, ethnicity/race (if applicable)
- Record relevant medical and surgical histories
- The subjects will be imaged using the VeriSight device according to the routine workflows
- Relevant imaging for each procedural steps will be recorded.
- The Investigator will grade the imaging recorded
- The corresponding clinical information and information about the use of device and system, including device deficiencies and safety-related adverse device effects related to VeriSight, will be recorded by the Investigator in the CRF
- The registry examinations including all collected de-identified images will be transferred to Philips

Document ID:	IGT_IGD_ICE Registry Study_2019_10745	Document title:		Classification:	Confidential
Modified:	24 APR 2021	Philips ICE Registry			
Version:	2.0	User Tool ID:	16.2.6UserTool0004	Page:	20
Status:	Final	User Tool Version Date	30May2019		

Clinical Registry Protocol
IGT_IGD_ICE Registry Study_2019_10745

- After the completion of the procedure, subject are dismissed from the registry after monitoring for post-procedure adverse device effects either at discharge or ≤48 hrs post-procedure, whichever is sooner.

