9.2. Informed Consent Process, Procedures, and Documentation

In obtaining and documenting informed consent, the investigator must comply with applicable regulatory requirements (e.g., 45 CFR Part 46, 21 CFR Part 50, 21 CFR Part 56) and should adhere to ICH GCP. Prior to the beginning of the registry, the investigator should have the IRB's written approval for the protocol and the written informed consent form(s), ICF and any other written information to be provided to the subjects. The consent form describes in detail the study, procedures, and risks. If new information becomes available during the course of the study that is relevant to the safety or well-being of the subjects, the consent form may be updated and presented to the subjects for review and consideration of continued participation. Consent forms will be provided to subjects in their native language and will be translated from the IRB approved version.

Study participation is voluntary. Potential subjects, and/or their legal representatives if subject is unable to consent on their own behalf, are given the most current IRB-approved consent form to read. They shall be provided ample time for review and an opportunity to ask questions about the study. If they agree to participate, they shall sign the consent form and be given a copy of the signed document for their records, along with any additional subject information. Each of these

Document ID:	IGT_IGD_ICE Registry Study 2019 10745	Document title:		Classification:	Confidential
Modified:	24 APR 2021	Philips ICE Registry			
Version:	2.0	User Tool ID:	16.2.6UserTool0004	Page:	28
Status:	Final	User Tool Version Date	30May2019		

Clinical Registry Protocol
IGT_IGD_ICE Registry Study_2019_10745

actions/steps shall be documented. Only after Informed Consent has been obtained, may the remaining study procedures begin.

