4.3 Selection of Study Population

All subjects age 18 and older that are scheduled for and will undergo a planned cardiac interventional percutaneous procedure in which the guidance of ICE is indicated, eligible and willing to sign an informed consent form without meeting any of the exclusion criteria set and

Document ID:	ICE VeriSight Registry SAP	Document title:		Classification:	For internal use
		Statistical Analysis Plan			
Modified:	02SEP2022			Author:	[name]
Version:	1.0	User Tool ID:	16.2.6UserTool0025	Approver:	[name]
Status:	Final	User Tool Version Date:	29Oct2019	Page:	7 of 16

Statistical Analysis Plan

meeting all the inclusion criteria set forth in the protocol will be included in the population for analyses. Those who sign consent but do not undergo a cardiac procedure utilizing the Philips ICE catheter will be excluded from the analyses (screen failures).

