8.2.1 Analysis Population

Since registry study is an observational study, no per protocol nor intent-to-treat population analyses is to be performed.

Document ID:	ICE VeriSight Registry SAP	Document title:	Classification:	For internal use
		Statistical Analysis Plan		
Modified:	02SEP2022		Author:	[name]
Version:	1.0	User Tool ID:	Approver:	[name]
Status:	Final	User Tool Version Date:	Page:	12 of 16

Statistical Analysis Plan

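### The only analysis population is defined by eligibility, so a patient enrolled and imaged with VeriSight who has an eligibility deviation can be left out of the primary performance and safety results.

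*Protocol*

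**What the plan says.** Protocol 8.2 gives one analysis population: adults scheduled for and undergoing an ICE-indicated procedure who are "without meeting any of the exclusion criteria set and meeting all the inclusion criteria set forth in the protocol will be included". SAP 4.3 repeats the rule, asking that the subject be "willing to sign an informed consent form without meeting any of the exclusion criteria set" and stating that those "meeting all the inclusion criteria set forth in the protocol will be included in the population for analyses". Both sections then exclude, as screen failures, consented subjects who do not have a procedure using the catheter.

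SAP 8.2.1, the section headed Analysis Population, names no set of its own. It says only that "no per protocol nor intent-to-treat population analyses is to be performed". Neither SAP 5.4 nor SAP 8.8 defines a separate safety population.

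Protocol 4.4 fixes enrollment at the moment the catheter is in the vasculature and on. Protocol 4.5 says: "Those who provide consent, but then are determined to be ineligible at the time of enrollment will be considered screen failures". Exclusion 1 in Protocol 4.2 covers contraindication to ICE catheter placement, or "patient considerations that make placement of VeriSight not technically feasible".

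Two statements point the other way. The Protocol summary says that every enrolled subject will be accounted for in the report, and Protocol 8.3 places the analyses on a real-world, all-comer population.

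**The concern.** Enrollment and exposure coincide in this registry. A rule that conditions analysis on eligibility, and not on enrollment, can therefore remove someone in whom the device was actually used. In a single-arm registry the primary outputs are simple proportions, so the denominator rule feeds straight into the headline figures. SAP 4.1 ties the analysis at 100 subjects to a CE mark submission, and Protocol 2.3 ties the registry to filings outside the US.

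The removal may also be related to outcome. Technical success requires the catheter to reach its target position in the heart. Exclusion 1 concerns whether placement is technically feasible in that patient. A case in which the catheter is in the vein and on but cannot be advanced fails the endpoint, and it is also the kind of case in which the patient's suitability for placement may be questioned afterwards. If such a case were treated as ineligible, a failure would leave both numerator and denominator. No planned analysis would show that this had happened: there is no second population, and SAP 8.2.2 says that the impact of missing data will not be evaluated.

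**Working it through.** The documents give no figure to reproduce. The sample size of up to 200 has no power or precision calculation behind it, and no expected number of eligibility deviations is stated. The check is therefore a reading of the text, followed by an illustration of size.

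**Text**

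1. Condition for analysis: all inclusion criteria and no exclusion criterion met (Protocol 8.2, SAP 4.3).
2. Condition for enrollment: device in the vasculature and on (Protocol 4.4). The two conditions differ, so a patient can satisfy the second and fail the first.
3. Ineligibility found at the time of enrollment makes a screen failure (Protocol 4.5). By step 2, that moment comes after insertion. Protocol 8.2 attaches the same label to a different group, those with no procedure using the catheter. The term therefore has two meanings.
4. Other sets that might hold this patient: none (SAP 8.2.1, 5.4, 8.8).
5. Data on this patient: device effects are collected from enrollment (Protocol 7.7), so the safety data would exist even if they were not analysed.

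**Size**

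Let *f* be the fraction of enrolled patients left out, *p_in* the success rate among those analysed and *p_out* the rate among those left out. The rate over all enrolled is *p_all* = (1 − *f*)·*p_in* + *f*·*p_out*, so the reported rate exceeds it by

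*p_in* − *p_all* = *f*·(*p_in* − *p_out*).

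Assume *p_in* = 97% and one patient in 100 left out. If that patient was a failure, the difference is 0.01 × (0.97 − 0) = 0.97 points. If a success, it is 0.01 × (0.97 − 1) = −0.03 points.

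Exact (Clopper-Pearson) 95% intervals, the method in SAP 8.7.1, with assumed counts and about 97% success among those analysed:

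| Enrolled | Left out | Left out of analysis | Restored, all failures | Restored, all successes |
|---|---|---|---|---|
| 100 | 1 | 96/99 = 97.0% (91.4–99.4) | 96/100 = 96.0% (90.1–98.9) | 97/100 = 97.0% (91.5–99.4) |
| 100 | 2 | 95/98 = 96.9% (91.3–99.4) | 95/100 = 95.0% (88.7–98.4) | 97/100 = 97.0% (91.5–99.4) |
| 100 | 5 | 92/95 = 96.8% (91.0–99.3) | 92/100 = 92.0% (84.8–96.5) | 97/100 = 97.0% (91.5–99.4) |
| 200 | 10 | 184/190 = 96.8% (93.3–98.8) | 184/200 = 92.0% (87.3–95.4) | 194/200 = 97.0% (93.6–98.9) |

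Starting from 95% success gives the same pattern: with one left out of 100, 94/99 = 94.9% against 94/100 = 94.0% or 95/100 = 95.0%.

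For safety, SAP 8.7.1 names the exact interval only for the three performance measures; I apply it to device events as an assumption. With no event among those analysed, the upper limit is 1 − 0.025^(1/*n*):

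- 100 enrolled, one left out: 0/99 has an upper limit of 1 − 0.025^(1/99) = 3.7%. If the omitted patient had an event, 1/100 has an upper limit of 5.4%.
- 200 enrolled, one left out: 0/199 has an upper limit of 1.8%, against 2.8% for 1/200.

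**The case against.** The strongest reply is that nothing orders the removal. Protocol 8.2 says that subjects meeting the criteria will be included; it does not say that only they will be. Its wording looks forward from screening, and the SAP puts it under selection of the study population. The one express exclusion covers consented subjects with no procedure using the catheter, which does not describe an imaged patient. With the all-comer statement in Protocol 8.3 and the refusal of a per-protocol set in SAP 8.2.1, a reader could conclude that every imaged patient is analysed. This reply stands in part: the omission is an inference. It does not remove the problem, because this is the only population defined and no passage places an enrolled, ineligible patient in it.

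Several stronger readings are tempting but not supported:

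- *Failed deliveries will be relabelled as ineligible.* Exclusion 1 is about patient considerations assessed at screening, and Protocol 6.4 records delivery and the number of attempts as procedural data. The overlap makes relabelling possible; nothing authorises it.
- *A thrombus first seen by VeriSight makes the patient ineligible.* Exclusion 3 is worded in terms of known conditions, and thrombus is also listed among the complications that VeriSight is to assess.
- *Consent through a legal representative (Protocol 9.2) creates biased removals.* That is a separate question of consent wording, with no shown link to success or event rates.
- *These patients go unfollowed.* Protocol 4.5 follows enrolled subjects, Protocol 7.7 collects device effects from enrollment, and Protocol 9.11 requires deviations to be recorded.
- *The one-time screening in Table 1 must change.* The 30 days are a maximum, and the analysis point does not depend on them.
- *The summary's promise to account for all enrolled subjects is contradicted.* Accounting for a subject is not the same as analysing that subject.

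**Conclusion.** The point holds as a gap in the definition of the analysis population, with a possible outcome-related exclusion. It is not a demonstrated removal of patients. Protocol 4.4, 4.5 and 8.2 and SAP 4.3, read together, allow an exposed and enrolled patient to be left out of the primary results, in tension with Protocol 8.3.

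The effect is bounded by the fraction left out, which the documents do not give and which may be small. With 1 to 5 of 100 enrolled left out, reported success is too high by about 1 to 5 points if all of them failed, and essentially unchanged if all succeeded. For rare device events, one omitted event matters more in relative terms. These sizes rest on assumed counts and an assumed success rate near 95–97%. No hypothesis or performance threshold is at stake, so the consequence is for the accuracy of the reported rates.

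**What to change.** In Protocol 8.2 and SAP 4.3, replace the eligibility condition with a statement that all consented subjects enrolled per Section 4.4 are included in all primary performance and safety analyses, regardless of any eligibility deviation found at or after enrollment. List those deviations. An eligible-only result may be added as a sensitivity analysis. SAP 8.2.1 can point to this definition.

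In Protocol 4.5, limit screen failure to consented subjects who do not reach the 4.4 enrollment point, and list separately any in whom insertion was attempted. Using the 4.4 point in both places leaves no patient between the two categories.

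The cost is a few sentences in each document, with no new data collection for the analysis itself, since device effects are already collected from enrollment and deviations already recorded. The downside is that reported rates may be slightly less favourable. The wording should be settled before results are reviewed.

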8.3. Statistical Analyses

No formal statistical hypothesis test is planned and the primary and secondary endpoints will be presented as descriptive statistics only. An interim analysis will be conducted following 100th patient enrollment to monitor, measure, and review performance and safety measures prior to determination of further enrollment in the registry.

Document ID:	IGT_IGD_ICE Registry Study 2019 10745	Document title:		Classification:	Confidential
Modified:	24 APR 2021	Philips ICE Registry			
Version:	2.0	User Tool ID:	16.2.6UserTool0004	Page:	27
Status:	Final	User Tool Version Date	30May2019		

Clinical Registry Protocol
IGT_IGD_ICE Registry Study_2019_10745

Statistical analyses will be done on the real-world, all-comer population and presented as descriptive statistics and 95% confidence intervals. Subject data from all clinical sites are intended to be pooled for analysis to broaden demographic representation. However, it is possible that sub-analyses may be conducted in a population stratified by procedure characteristics and baseline characteristics.

9. SUPPORTING DOCUMENTATION AND OPERATIONAL CONSIDERATIONS

9.1. Regulatory, Ethical, and Study Oversight Considerations

This registry will be conducted in accordance with the relevant parts of the Code of Federal Regulations (21 CFR 11, 50, 56), ISO 14155:2011, the ICH-E6 Guidelines for GCP, the Declaration of Helsinki (2013). Additional state and local regulations will be followed when applicable.

Investigators and sites are required to have the protocol, informed consent forms, and any other materials related to this study plan approved by the IRB. Any additional requirements imposed by the IRB shall be followed. Any amendments to the protocol must be reviewed and approved by the study Sponsor, and subsequently, by the designated IRB, according to the approval committee's requirements. Prior to enrollment, the Sponsor or designee will review the written approvals for completeness, including the required elements of the consent form, and the Sponsor will provide protocol and study administration training. The continued eligibility for participation by an investigator and the institution requires maintenance of all approvals (e.g. annual reviews, amendment reviews).

Each subject will provide written, informed consent as outlined in **Section 9.2** prior to any study activities taking place.

9.2. Informed Consent Process, Procedures, and Documentation

In obtaining and documenting informed consent, the investigator must comply with applicable regulatory requirements (e.g., 45 CFR Part 46, 21 CFR Part 50, 21 CFR Part 56) and should adhere to ICH GCP. Prior to the beginning of the registry, the investigator should have the IRB's written approval for the protocol and the written informed consent form(s), ICF and any other written information to be provided to the subjects. The consent form describes in detail the study, procedures, and risks. If new information becomes available during the course of the study that is relevant to the safety or well-being of the subjects, the consent form may be updated and presented to the subjects for review and consideration of continued participation. Consent forms will be provided to subjects in their native language and will be translated from the IRB approved version.

Study participation is voluntary. Potential subjects, and/or their legal representatives if subject is unable to consent on their own behalf, are given the most current IRB-approved consent form to read. They shall be provided ample time for review and an opportunity to ask questions about the study. If they agree to participate, they shall sign the consent form and be given a copy of the signed document for their records, along with any additional subject information. Each of these

Document ID:	IGT_IGD_ICE Registry Study 2019 10745	Document title:		Classification:	Confidential
Modified:	24 APR 2021	Philips ICE Registry			
Version:	2.0	User Tool ID:	16.2.6UserTool0004	Page:	28
Status:	Final	User Tool Version Date	30May2019		

Clinical Registry Protocol
IGT_IGD_ICE Registry Study_2019_10745

actions/steps shall be documented. Only after Informed Consent has been obtained, may the remaining study procedures begin.

Patients scheduled for percutaneous cardiac intervention procedure and not contraindicated for ICE use will be asked to provide consent to use their data. Patients who agree to study participation must sign an IRB-approved ICF. Subjects will be informed that their participation in this study is voluntary and they may refuse to participate or discontinue from the study at any time. Subjects may withdraw from the study at their own request or at the request of their legally acceptable representative. The sponsor must be informed in each withdrawal case. The reason for withdrawal must be recorded in the eCRF and in the patient medical record.

9.3. Registry Discontinuation and Closure

When a registry is prematurely terminated, refer to **Section 4.7**, for handling of enrolled study subjects.

This study may be temporarily suspended or prematurely terminated if there is sufficient reasonable cause. Written notification, documenting the reason for study suspension or termination, will be provided by the Sponsor to the study Principal Investigators. If the study is prematurely terminated or suspended, the Principal Investigator (PI) will promptly inform study subjects, the Institutional Review Board (IRB), and will provide the reason(s) for the termination or suspension.

Circumstances that may warrant termination or suspension include, but are not limited to:

- Determination of unexpected, significant, or unacceptable risk to subjects
- Demonstration of efficacy that would warrant stopping
- Insufficient compliance to protocol requirements
- Data that are not sufficiently complete and/or evaluable
- Determination that the primary endpoint has been met
- Determination of futility

Study may resume once concerns about safety, protocol compliance, and data quality are addressed, and satisfy the Sponsor, IRB and/or Food and Drug Administration (FDA).)

9.4. Confidentiality and Privacy

This registry protocol, its associated methodologies, study devices, study-generated data, and the data management system contain confidential and proprietary information. Subject confidentiality will be maintained according to the Health Insurance Portability and Accountability Act of 1996 (HIPAA). Release of such information outside the scope of planned study operation is prohibited. All federal and local laws regarding protection of patient confidentiality will be followed, as well as any additional site-specific requirements that may be required. Personal Health Information (PHI) will be acquired during the consenting process of the subject and from the medical records. All data

Document ID:	IGT_IGD_ICE Registry Study 2019 10745	Document title:		Classification:	Confidential
Modified:	24 APR 2021	Philips ICE Registry			
Version:	2.0	User Tool ID:	16.2.6UserTool0004		
Status:	Final	User Tool Version Date	30May2019	Page:	29

Clinical Registry Protocol IGT_IGD_ICE Registry Study_2019_10745

will be de-identified at each site before being entered into EDC. Individual subjects and their research data will be identified by a unique study identification number. The protocol, documentation, data, and all other information generated will be held in strict confidence to the extent allowed by law, including PHI. At the end of the study, all study databases will be de-identified and archived by the Sponsor.

The study monitor, Sponsor and other authorized representatives of the sponsor, representatives of the Institutional Review Board (IRB), or regulatory agencies may inspect all documents and records required to be maintained by the investigator, including but not limited to, medical records (office, clinic, or hospital) for the subjects in this study. The clinical study site will permit access to such records.

The study subject's contact information will be securely stored at each clinical site for internal use during the study. At the end of the study, all records will continue to be kept in a secure location for as long a period as dictated by the reviewing IRB, Institutional policies, or Sponsor requirements.

